4.3 Criteria for Subsequent Therapy

All patients must meet the minimal criteria for subsequent therapy: the absolute neutrophil count $\geq 1,000 / \mu\text{L}$, the platelet count $\geq 50,000 / \mu\text{L}$, and the resolution of toxicity to $\leq \text{Grade 1}$, pre-therapy baseline, or Grade 2 that is not clinically significant. Toxicities are graded by using NCI CTCAE v5.0 toxicity criteria.

In general, treatment should be on hold if the minimal criteria for subsequent therapy are not met. However, the patient may resume therapy if and when the physician and the patient believe that further treatment will benefit the patient. Supportive care will be allowed according to good clinical practice.

Remote Procedures

In case of any unexpected incidents that patients can't come back to MD Anderson Cancer Center for study treatment and assessments, remote procedures can be applied for this trial conduction, including remote consent, remote toxicity assessment via phone calls, virtual visit, etc., with compliance with institutional policies. Patients can have lab work, scheduled scans, physical exams and receive treatment locally if applicable. Laboratory work done at an outside facility is to be forwarded to the subject's attending physician at MD Anderson or the PI of the study, who will date and sign off on the labs to verify the results were reviewed. Remote monitoring can be applied as needed. Study drug may be mailed to the patient per institutional guidelines/approval.

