In the event of a dosing delay up to 12 hours after the scheduled dosing time, the patient should still take that day's dose. If the dosing delay continues for >12 hours after the scheduled dosing time, or if the patient vomits after a dose, the patient should skip dosing for that day and not make up for it the following day.

Recommended Dose Modifications for Futibatinib

Stepwise dose reductions of 4 mg to 16 mg (first reduction) and 12 mg (second reduction) are permitted based on toxicities. If dose reduction fails to result in achieving the minimal criteria to resume treatment or, if toxicities occur which would necessitate reduction of the dose of futibatinib below 12 mg QD, the patient should be discontinued from futibatinib.

Following a dose reduction, if a benefit/risk assessment favors an increase of futibatinib dose up to the initial starting dose an agreement with the Sponsor's medical monitor is required prior to the dose increase.

If toxicities do not recover based on the criteria defined below within 28 days after the last dose of futibatinib, the patient will be discontinued permanently from treatment. If resumption criteria are met within 28 days of the last dose of futibatinib, the patient may resume futibatinib treatment at the appropriate dose level.

Dose Modifications for Nonhematologic Toxicities

Dosing modification guidelines for nonhematologic and eye toxicities are provided in **Table 4**

Please see futibatinib package insert for details.

(https://www.accessdata.fda.gov/drugsatfda_docs/label/2022/214801Orig1s000lbl.pdf)

Table 4: Recommended Dose Modifications for Related Nonhematologic Toxicities

Adverse Reaction	Severity	Futibatinib Dosage Modifications
Retinal Pigment Epithelial Detachment (RPED)	Not applicable	
Continue at the current dose and continue periodic ophthalmic evaluation:
 
 • If resolving within 14 days, continue at the current dose. • If not resolving within 14 days, withhold until resolving; then resume at previous or a lower dose

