Hyperphosphatemia	
Serum phosphate $\geq 5.5 - \leq 7$ mg/dL
 
Serum phosphate $> 7 - \leq 10$ mg/dL
 
Serum phosphate >10 mg/dL
	
Continue at the current dose and initiate phosphate lowering therapy. Monitor serum phosphate weekly.
 
• Initiate or adjust phosphate lowering therapy. Monitor serum phosphate weekly and Dose reduced to next lower dose
 
 - If the serum phosphate resolves to ≤ 7 mg/dL within 2 weeks after dose reduction, continue at this reduced dose. - If serum phosphate is not ≤ 7 mg/dL within 2 weeks, further reduce to the next lower dose. - If serum phosphate is not ≤ 7 mg/dL within 2 weeks after the second dose reduction, withhold until serum phosphate is ≤ 7 mg/dL and resume at the dose prior to suspending. 
Initiate or adjust phosphate lowering therapy and monitor serum phosphate weekly and
 
 • Withhold until phosphate is ≤ 7 mg/dL and resume at the next lower dose. - Permanently discontinue if serum phosphate is not < 7 mg/dL within 2

		weeks following 2 dose interruptions and reductions.
Other Adverse Reactions	Grade 3 ^a	Withhold until toxicity resolves to Grade 1 or baseline, then resume - for hematological toxicities resolving within 1 week, at the dose prior to suspending. - for other adverse reactions, at next lower dose.
	Grade 4 ^a	Permanently discontinue

^a Severity as defined by National Cancer Institute Common Terminology Criteria for Adverse Events (NCI CTCAE version 5.0).

Dose Modifications for Hematologic Toxicities are presented in [Table 5](#).

Table 5: Futibatinib Dose Interruption and Modification for Related Hematologic Toxicities

CTCAE Grade (value)	Recommended dose modification any time during a cycle of futibatinib ^a
Anemia (Hgb)	
Grade 1 (Hgb < LLN - 10.0 g/dL)	Maintain dose level
Grade 2 (Hgb < 10 – 8.0 g/dL)	Maintain dose level
Grade 3 (Hgb < 8.0 - 6.5 g/dL)	Withhold dose until resolved to ≤ Grade 1 or baseline, • If resolved ≤7 days, then maintain dose level • If resolved >7 days, then reduce 1 dose level
Grade 4 (life threatening consequences; urgent intervention indicated)	Withhold dose until resolved to ≤ Grade 1 or baseline, then reduce 1 dose level
Neutropenia (ANC)	
Grade 1 (ANC < LLN - 1500/mm ³)	Maintain dose level
Grade 2 (ANC < 1500 - 1000/mm ³)	Maintain dose level
Grade 3 (ANC < 1000 - 500/mm ³)	Maintain dose level

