Grade 4 (ANC < 500/mm ³)	Withhold dose until resolved to ≤ Grade 2 or baseline, • If resolved ≤7 days, then maintain dose level • If resolved >7 days, then reduce 1 dose level
Febrile neutropenia: ANC < 1000/mm ³ , and with a single temperature > 38.3°C (101°F) or a sustained temperature ≥ 38°C (100.4°F) for more than one hour.	Withhold dose until resolved, then reduce 1 dose level
Thrombocytopenia	
Grade 1 (PLT < LLN - 75,000/mm ³)	Maintain dose level
Grade 2 (PLT < 75,000 - 50,000/mm ³)	Maintain dose level
Grade 3 (PLT < 50,000 - 25,000/mm ³)	Withhold dose until resolved to ≤ Grade 1 or baseline, • If resolved ≤7 days, then maintain dose level • If resolved >7 days, then reduce 1 dose level
Grade 4 (PLT < 25,000/mm ³)	Withhold dose until resolved to ≤ Grade 1 or baseline, then reduce 1 dose level

Abbreviations: ANC=absolute neutrophil count; CTCAE=Common Terminology Criteria for Adverse Events; Hgb=hemoglobin; LLN=lower limit of normal; PLT=platelets.

a. Interrupt futibatinib if any toxicities are intolerable, regardless of the grade (including Grade 1 and 2). If or when the toxicity resolves to a tolerable state, consideration can be given to resuming futibatinib at the same dose if deemed appropriate or reduced by one dose level if needed.

Dose Modifications in Case of Induced Drug Liver Injury (Hy's Law)

Futibatinib will be permanently discontinued (pembrolizumab is allowed to be administered as a single agent if there is no tumor progression and no pembrolizumab related prohibitive toxicity) if liver function test abnormalities fulfill Hy's Law criteria defined as concurrent observation of the following, with no other reason found to explain the findings (such as viral hepatitis A, B, or C; preexisting or acute liver disease; liver metastases; or another drug capable of causing the observed liver injury):

- Elevated aminotransferase enzymes of $>3 \times$ ULN (upper limit of normal)
- Alkaline phosphatase (ALP) $<2 \times$ ULN
- Associated with an increase in bilirubin $\geq 2 \times$ ULN

Dose Delays and Interruptions Specific for Pembrolizumab

Description of Pembrolizumab: please see pembrolizumab packaging insert.

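### Table 4, Table 5 and Section 4.3 give inconsistent futibatinib instructions for Grade 4 cytopenias and Grade 3 neutropenia, and no rule says which governs

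*Combined protocol and SAP*

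**What the plan says.** Three places in the protocol tell the site what to do with futibatinib when a blood count falls.

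- **Section 4.4, Table 4.** The caption limits it to nonhematologic events: "Table 4: Recommended Dose Modifications for Related Nonhematologic Toxicities". The heading above it and the sentence introducing it do the same. Its Other Adverse Reactions row nevertheless addresses hematologic events. At Grade 3 the row says "Withhold until toxicity resolves to Grade 1 or baseline, then resume", and the resumption dose is then split, with one branch reading "for hematological toxicities resolving within 1 week, at the dose prior to suspending". At Grade 4 the row says only "Permanently discontinue".
- **Section 4.4, Table 5.** The caption is "Table 5: Futibatinib Dose Interruption and Modification for Related Hematologic Toxicities", and the text directs hematologic toxicity here. It applies at any time in a cycle. For Grade 4 anemia and Grade 4 thrombocytopenia it says "Withhold dose until resolved to ≤ Grade 1 or baseline, then reduce 1 dose level". For Grade 4 neutropenia it says "Withhold dose until resolved to ≤ Grade 2 or baseline", with the same dose if resolved in 7 days or less and one level lower otherwise. For Grade 3 neutropenia (ANC 500 to below 1,000) the dose is kept.
- **Section 4.3.** Subsequent therapy requires ANC of at least 1,000, platelets of at least 50,000, and toxicity resolved to Grade 1, to baseline, or to a Grade 2 that is not clinically significant. In general "treatment should be on hold if the minimal criteria for subsequent therapy are not met", but physician and patient may agree to resume.

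**The concern.** A Grade 4 cytopenia is a permanent stop on the face of one table and a temporary hold in the other. The Grade 4 line of Table 4 sits directly beneath a line that deals with hematologic events by name, so a reader has no textual reason to assume that it leaves them out. No sentence says which table prevails.

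Separately, Grade 3 neutropenia on the first day of a later cycle meets an instruction to keep dosing in Table 5 and an instruction to hold in Section 4.3.

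What is at stake is patient safety and uniform handling. Two patients with the same count could be managed in opposite ways, and one of the possible outcomes is irreversible for that patient.

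**Working it through.** No arithmetic underlies the point, and the plan states no figure to reproduce. The check is a comparison of the futibatinib instruction for each event and grade.

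| Event | Table 4, Other Adverse Reactions (if it applies) | Table 5 | Section 4.3 |
|---|---|---|---|
| Grade 4 anemia | Permanent stop | Withhold to Grade 1 or baseline, then one level lower | No hemoglobin threshold; general toxicity-grade criterion only |
| Grade 4 thrombocytopenia | Permanent stop | Withhold to Grade 1 or baseline, then one level lower | Platelets at least 50,000 plus the toxicity-grade criterion |
| Grade 4 neutropenia | Permanent stop | Withhold to Grade 2 or baseline; same dose if 7 days or less, otherwise one level lower | ANC at least 1,000 |
| Grade 3 neutropenia | Withhold to Grade 1 or baseline | Dose unchanged | Hold below ANC 1,000, with override |
| Grade 3 anemia | Withhold to Grade 1 or baseline; same dose if within 1 week, otherwise one level lower | Same | General toxicity-grade criterion only |
| Grade 3 thrombocytopenia | Withhold to Grade 1 or baseline; same dose if within 1 week, otherwise one level lower | Same | Platelets at least 50,000 plus the toxicity-grade criterion |

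The comparison gives four results.

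1. **Grade 4, all three cytopenias.** Tables 4 and 5 conflict if the Table 4 row is read as it stands. Section 4.3 is not part of this conflict. It sets a floor and contains no permanent stop, so it is compatible with Table 5.
2. **Grade 3 neutropenia.** Take ANC 800 on day 1 of a later cycle. Table 5 keeps the dose, because 800 lies between 500 and 1,000. Section 4.3 in general holds, because 800 is below 1,000. Table 4, if it applies, withholds until ANC reaches 1,500 (the Grade 1 boundary in Table 5) or baseline. If Table 4 is set aside, Table 5 and Section 4.3 still disagree. For a patient who entered at the eligibility minimum of ANC 1,000 (Section 3.1), the baseline target in Table 4 coincides with the Section 4.3 threshold, and only Table 5 differs.
3. **Grade 3 anemia and thrombocytopenia.** Tables 4 and 5 agree, reading slower hematologic recovery as falling under Table 4's next-lower-dose branch.
4. **Timing.** Section 4.3 concerns subsequent therapy and Table 5 any time in a cycle, so those two collide mainly at the start of a later cycle.

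**Frequency.** Table 2 in Section 2.4 lists preferred terms seen in at least 20% of 13 patients on this combination. Since 0.20 × 13 = 2.6, an unlisted term occurred in at most 2 of 13 patients (2/13 = 15.4%). No cytopenia is listed. The bound applies to each term separately, covers all grades, and rests on 13 patients. The documents give no cytopenia rate for the combination.

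**The case against.** The best answer is that Table 5 plainly governs. Heading, lead-in and caption all confine Table 4 to nonhematologic events, and the text then sends hematologic events to Table 5. On that view the hematologic phrase in the Grade 3 cell is a leftover, and the Grade 4 line never reached cytopenias. This is a reasonable reading, and it makes the Grade 4 conflict one of unclear scope. It does not settle the matter, because the row departs from its own caption and no precedence is stated. It also leaves the Grade 3 neutropenia conflict with Section 4.3 untouched.

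The protocol is also flexible. Section 4.3 speaks in general terms and has an override, and Section 4.4 calls its rules general guidelines and lets physicians add remedies. That softens the practical effect, but it does not make the default instructions consistent.

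A reader might infer more than the documents support:

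- **That every hematologic toxicity has three incompatible rules.** Only Grade 3 neutropenia can meet three different instructions.
- **That the platelet minimum of 50,000 in Section 4.3 contradicts the stricter recovery target in Table 5.** Section 4.3 states a minimum and adds a toxicity-grade criterion. A stricter rule above a floor is not a contradiction.
- **That one laboratory value could mean uninterrupted full dosing or a permanent stop.** Every Grade 4 row in Table 5 begins with a hold, and no passage permanently stops futibatinib for Grade 3 neutropenia as such.
- **That a primary endpoint is distorted.** The primary safety endpoint in Section 1.2 is adverse events and serious adverse events, and Section 7.2 plans a description by grade, type and dose level. Discontinuation rate is not a named endpoint, and treatment deviations do not remove patients from the response analysis.

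**Conclusion.** The point holds in limited form. Two inconsistencies stand in the current text. The first is Grade 4 anemia, neutropenia and thrombocytopenia, between Tables 4 and 5. It rests on reading the Other Adverse Reactions row as covering hematologic events at Grade 4 as it does at Grade 3, a reading that the row invites and the caption resists. The second is Grade 3 neutropenia at the start of a later cycle, between Table 5 and Section 4.3 on any reading, with Table 4 as a third instruction if its row applies.

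The consequence is for patient safety and consistent handling. A patient could be permanently stopped or resumed according to the table consulted. The number affected is probably small on the Table 2 evidence but cannot be stated. The sample size, type I error and power in Section 7.1 do not depend on the point.

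**What to change.** Reconcile Table 4, Table 5 and Section 4.3. State, for each hematologic event and grade, which passage governs, and word the Other Adverse Reactions row so that its scope is clear at both Grade 3 and Grade 4. Make the ANC hold and resume criteria in Section 4.3 and the governing table agree at the start of a cycle. Which clinical rule applies is for the sponsor to decide, and nothing here favours one over another.

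The cost is a wording amendment to two tables and one paragraph. It adds no patients, visits or procedures and does not change the statistical design.

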Patients are not permitted to receive any other investigational or any other anticancer therapy, including chemotherapy, immunotherapy, biological response modifiers, or antineoplastic endocrine therapy during the study treatment period.

Extended-field radiation therapy or palliative radiation to a focal site of measurable disease is also prohibited. If it is deemed in the best interest of the patient and after discussion between the Investigator and Medical Monitor, it can be administered, but the patient will be censored for the primary endpoint analysis.

Immunosuppressive therapy including steroids (> 10 mg/day prednisone or equivalent) is not permitted with pembrolizumab.

Concomitant strong inhibitors and inducers and sensitive substrates of CYP3A4 should be avoided, if possible, with futibatinib. Caution is advised if these drugs are given concomitantly (see [Appendix A: CYP3A4 and Transporters – Classification of Substrates, Inhibitors, and Inducers of CYP Enzymes and Transporters](#)). Alternative replacement is highly recommended.

Concomitant Medications and Therapies Requiring Precautions

Supportive treatment is allowed based on available institutional or local guidelines.

Local or regional palliative cryotherapy or radiation, such as for bone pain or palliative surgery (non-anti-neoplastic intent), are permitted (provided the target lesion is not a site of measurable disease and is not indicative of disease progression). Study therapy should be ceased a minimum of 2 days prior to administration of palliative treatment, and may be resumed 7 days after the procedure or when the patient has recovered from the side effects of the procedure.

The following medications/therapies may be given concomitantly under the following guidelines:

Hematologic Support: may be administered as medically indicated (that is, blood transfusions, granulocyte colony-stimulating factor, erythropoietin stimulating agents) according to the institutional site standards or American Society of Clinical Oncology (ASCO) guidelines ⁷⁶.[76].

Management of Diarrhea: Prophylactic treatment for diarrhea is permitted during the study if clinically indicated according to the institutional or published guidelines ⁷⁷.

Management of Nausea/Vomiting: Antiemetics may be administered as clinically indicated according to institutional standards or ASCO guidelines ⁷⁸.

Drug Interactions

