CR = complete response, PR = partial response, SD = stable disease, PD = progressive disease, and NE = not evaluable.

If a CR is met at the first time point, then any disease seen at a subsequent time point, even disease meeting PR criteria relative to baseline, makes the disease PD at that time point (since disease must have reappeared after CR). Best response would depend on whether the minimum duration for SD was met. However, sometimes "CR" may be claimed when subsequent scans suggest small lesions were likely still present and, in fact, the patient had a PR, not a CR at the first time point. Under these circumstances, the original CR should be changed to PR and the best response is a PR.

Efficacy analysis: All patients who have received one dose of any study agent will be considered evaluable for efficacy. Patients who are removed from the study before the first scheduled restaging workup because of progression, serious drug-related adverse events, or any other reasons are also considered evaluable for efficacy. If the restaging workups are not done, these patients will be denoted the same as the patients who have new lesions.

Other Assessment

Patients' functional performance status will be graded according to ECOG criteria as seen [ATTACHMENT B](#).

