7 STATISTICAL CONSIDERATIONS

7.1 Study Design

After patients have signed the informed consent, patients will be enrolled to receive therapy for toxicity and efficacy evaluation. One cycle of therapy is 21 days. No randomization is utilized to assign patients in this study.

The DLT window is 21 days after starting the treatment. The trial starts with safety lead-in:

- Six lead-in patients will be enrolled at dose level 1. If there is one or less DLT, the study will continue following a Bayesian optimal phase 2 (BOP2) design.
- If there are two or more DLTs, the study will enroll another six lead-in patients at dose level -1.
- If there are two or more DLTs at dose level -1, the study of that therapy will be terminated.
- If there is one or less DLT, the study will follow a BOP2 design at the dose level -1.
- The lead-in patients are allowed to be counted as the patients enrolled to stage I per a BOP2 design if they initiate the same dose.

The intent-to-treat (ITT) population includes all patients who have received study agents. Efficacy will be analyzed based on the ITT population, following a BOP2 design ^{86,87} with p_0 (historical response rate) = 15% and p_1 (minimum desired experimental response rate) = 40%. The first stage will consist of 12 patients. Accrual will stop at the end of the first stage if fewer than 3 responses are seen. The second stage will consist of 12 patients. We will declare the experimental agent worthy of further study if 7 or more responses are seen in 24 patients. This design has a Type I error rate of 4.9% and an 86% power. The maximum number of patient enrollment is $6 + 24 = 30$, noting that the lead-in patients will be counted as phase II patients.

Below are the operating characteristics of the design using the BOP2 web application, (Table 11), which is available at <http://www.trialdesign.org>.

Table 11: The Operating Characteristics Of The BOP2 Design For This Study

Scenario	Response Rate	Early Stopping (%)	Claim Promising (%)	Average Sample Size
1	0.15	73.58	4.87	15.2
2	0.30	25.28	55.61	21.0
3	0.40	8.34	86.20	23.0
4	0.50	1.93	97.38	23.8

During the phase II part, after 6 patients are treated, at any time > 30% of patients have DLTs, that dose level will be terminated.

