7.2 Statistical Analyses

All patients will be evaluated for toxicity and efficacy from the time of their first treatment. All patients must be assessed for response to treatment to be assigned one of the following categories, even if there are major protocol treatment deviations or if they are ineligible.

- 1) Complete response
- 2) Partial response
- 3) Stable disease
- 4) Progressive disease
- 5) Early death from malignant disease
- 6) Early death from toxicity
- 7) Early death because of other cause
- 8) Unknown (not assessable, insufficient data)

Categorization of response will be based on RECIST 1.1. All of the patients who meet the eligibility criteria (with the possible exception of those who received no study medication) will be included in the main analysis of the response rate. Patients in response categories 4-8 as above should be considered as failing to respond to therapy (disease progression). A patient will be determined as having a response if he/she has CR or PR during the initial 6 months of therapy; a patient will be determined as a non-response if there is no evidence of response by 6 months during this study. Thus, an incorrect treatment schedule or drug administration does not result in exclusion from the analysis of the response rate. In computing PFS and OS, withdrawing patients will be censored at the time of withdrawal.

Wilcoxon's Signed-Rank Test and Fisher's exact test will be used for data analysis of continuous variables and categorical variables, respectively. A mixed model accounting for patient effects will be used to analyze longitudinal data (including biomarker data) over time. For the objective of describing the toxicity profile, descriptive statistics will be provided on the grade and type of toxicity by dose level. The Kaplan-Meier method will be used to estimate PFS and OS.

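### Section 4.4 censors patients given otherwise prohibited radiation from a yes/no response endpoint; read as removal, this contradicts the all-treated efficacy set in 5.5 and 7.1

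*Combined protocol and SAP*

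**What the plan says.** Section 4.4 (Prohibitive Medications and Therapies) bars two kinds of radiation during treatment: extended-field, and palliative to a focal site of measurable disease. If either is nevertheless judged to be in the patient's interest, after discussion with the medical monitor, "it can be administered, but the patient will be censored for the primary endpoint analysis". Section 1.2 lists two primary endpoints, response and adverse events, and the clause does not say which it means. This point concerns response.

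The efficacy rules stand elsewhere:

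- **Section 7.1**, analysis set: "The intent-to-treat (ITT) population includes all patients who have received study agents". Efficacy is analysed in that set.
- **Section 7.1**, decisions: "Accrual will stop at the end of the first stage if fewer than 3 responses are seen"; "We will declare the experimental agent worthy of further study if 7 or more responses are seen in 24 patients".
- **Section 5.5**, efficacy analysis: "All patients who have received one dose of any study agent will be considered evaluable for efficacy". This includes patients taken off study before the first restaging for any reason.
- **Section 7.2**: every patient gets one of eight response categories despite major treatment deviations, and "Patients in response categories 4-8 as above should be considered as failing to respond to therapy". Category 8 is the unknown or unassessable group. Response means CR or PR within the first 6 months of therapy.
- **Section 7.2**, the only other censoring rule: "In computing PFS and OS, withdrawing patients will be censored at the time of withdrawal". PFS and OS are exploratory endpoints.

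**The concern.** Censoring has a meaning for a time-to-event endpoint. It has none for a response that is counted yes or no, unless the plan supplies one, and this plan does not. Because the clause censors the patient, not the later scans, an analyst may well read it as removal from the analysis. That reading conflicts with 5.5, 7.1 and 7.2, and no section says which rule prevails.

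The other possible reading is that assessments stop at the radiation and the patient stays in the denominator. Section 7.2 would then settle the outcome: a response already achieved counts, and otherwise the patient is a non-responder. No section says this either. It also leaves open whether a response first seen before radiation can be confirmed afterwards, although 5.5 requires confirmation at least 4 weeks later.

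Two analysts could therefore report different response rates from the same data and, on a boundary, different conclusions. The trial is open-label and the radiation is chosen after treatment starts, so removal is unlikely to be unrelated to how the tumour is behaving.

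**Working it through.** **Inputs.** From 7.1: stage 1 n = 12, continue with at least 3 responses; stage 2 n = 12, success with at least 7 of 24; null rate 15%, target rate 40%. Assumed: one or two affected patients, since the documents give no figure.

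**1. Reproduce the plan's figures.** For stage sizes n1 and n2,

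OC(p; n1, n2) = Σ over x = 3 to n1 of P[Bin(n1, p) = x] × P[Bin(n2, p) ≥ 7 − x].

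At p = 0.15 with (12, 12), the terms for x = 3, 4, 5, 6 and ≥ 7 are 0.01586 + 0.01804 + 0.01073 + 0.00340 + 0.00067 = 0.0487. At p = 0.40 the sum is 0.8620. Both match Table 11 (4.87% and 86.20%).

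**2. A non-responder is removed, no replacement, cutoffs fixed.** The response count does not change, so neither decision changes. Only the reported rate moves: 6/24 = 25.0%, 6/23 = 26.1%, 6/22 = 27.3%.

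**3. A responder is removed, no replacement.** 3/12 (continue) becomes 2/11 (stop); 7/24 (success) becomes 6/23 (not success). For one patient removed at random:

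- Interim: P[Bin(12, p) = 3] × 3/12. At 40%: 0.1419 × 0.25 = 3.5%. At 30%: 0.2397 × 0.25 = 6.0%.
- Final, stage 2 patient removed: Σ over x = 3 to 7 of P[Bin(12, p) = x] × P[Bin(12, p) = 7 − x] × (7 − x)/12. At 40%: 0.01007 + 0.00755 + 0.00242 + 0.00026 + 0 = 2.0%. At 30%: 3.7%.

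These are conditional on one such patient existing. The overall chance is smaller by the probability that anyone receives the prohibited radiation, which the documents do not give.

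**4. Random removal and the operating characteristics, cutoffs fixed, no replacement.**

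| Removed | Type I error | Power |
|---|---|---|
| none | 4.87% | 86.2% |
| 1 in stage 2 | 4.08% | 84.2% |
| 2 in stage 2 | 3.35% | 81.5% |
| 1 in stage 1 | 3.78% | 81.7% |
| 2 in stage 1 | 2.85% | 75.9% |

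**5. Removed non-responders are replaced.** Suppose the true rate in all treated patients is 15% and all k removed patients are non-responders. The rate among the 24 retained is then 0.15 × (24 + k)/24: 0.15625 for k = 1 and 0.1625 for k = 2. Putting these into OC(p; 12, 12) gives type I errors of 5.9% and 7.0%.

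**The case against.** The best defence is that the statistical section already gives one answer. All treated patients are analysed, every patient gets a category, and unassessable patients are failures. On that view the word in 4.4 is loose drafting in a concomitant-therapy section and cannot override 7.1. It stands to this extent: the contradiction depends on reading the clause as removal, and the alternative reading fits 5.5, 7.1 and 7.2. It does not dispose of the point, because 4.4 is the specific rule for these patients and nothing says that it yields.

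The defence is also right that the effect is small. A move from 25.0% to 26.1% is slight beside the exact 95% interval for 6/24, about 10% to 47%, and the radiation is prohibited by default.

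A reader might infer four stronger things that the documents do not support:

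- **That every irradiated patient is affected.** The clause covers only the otherwise prohibited radiation. The same section separately permits some palliative radiation, with no censoring.
- **That the false-positive rate is inflated as the plan stands.** With the stated cutoffs and no replacement it falls (step 4). It rises only if removed non-responders are replaced. Section 5.6 provides replacement only for lead-in patients not evaluable for DLT. However, 7.3 ties the interim summary to the first 12 evaluable patients, so accrual to 12 after a removal is not expressly ruled out.
- **That correcting the clause recovers the power lost in step 4.** At fixed cutoffs a removed patient and a counted non-responder both add nothing to the count, so the decision is the same. Power is recovered only for patients whose response can be credited.
- **That the chance of a boundary result is the chance of a reversal.** At a true rate of 40%, exactly 3/12 has probability 14.2%, and passing the interim with exactly 7/24 has 7.8% (24.0% and 14.3% at 30%). A reversal also needs the removed patient to be a responder, which gives the lower figures in step 3.

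**Conclusion.** The point holds in a limited form. The clause applies an undefined operation to the primary response endpoint and, read as removal, contradicts the plan's own analysis set and failure rule. The expected effect is modest. Without replacement, it is about one or two percentage points on a reported rate of 25%, and for one randomly removed patient a 2.0% to 6.0% chance of reversing a decision, for true rates of 30% to 40%. With replacement of one or two removed non-responders, type I error would be 5.9% or 7.0% against 4.87%.

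These figures rest on the assumed one or two patients, on fixed cutoffs, and in step 3 on removal unrelated to response. The text should be corrected, because in a 24-patient single-arm trial one responder can decide the result and the rule should be set before the data are seen.

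**What to change.** In Section 4.4, replace the censoring clause with wording to this effect: *the patient remains in the all-treated denominator (7.1) and is not replaced; response is determined under 7.2 from assessments before the radiation, and a patient without a qualifying CR or PR on that basis is a non-responder.* State also whether a response first seen before the radiation may be confirmed, as 5.5 requires, by later scans. A response rate that leaves these patients out may be reported as a labelled sensitivity analysis.

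The statements on local therapy in 4.2, in the opening of 4.4, and in the prohibited and permitted lists of 4.4 must be reconciled, because together they decide whom the clause covers. Which clinical rule applies is for the sponsor.

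The cost is wording only, with no extra patients or visits. The 3/12 and 7/24 rules stay as they are. The reported response rate may be slightly lower than with these non-responders left out, and a response first seen after the radiation earns no credit.
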